## 5.2 Randomization and Subject Numbering

This is a randomized, triple-blind, dose comparison study with an open-label cross-over segment. For Stage 1, a randomization list will be prepared at the beginning of the study. Another list will be created to replace subjects who withdraw from the study and are unblinded. Each participant will be assigned to one of the three dose conditions; 30 mg (low dose), 75 mg (medium-dose) or 125 mg (full dose). Twelve participants will be assigned to the full-dose condition, six participants to the 75 mg condition and six participants to the 30 mg low dose condition. The study will employ a blinded randomization procedure that will maintain the 2:1:1 ratio while maintaining the blind and ensuring that each subsequent condition assignment is not predicated on the previous assignment. Drug containers will be assigned a unique random number. At least 24 hours before each experimental session, container assignments to each subject will be performed on a per experimental session basis, and the container will contain the initial and supplemental capsules for a single experimental session. This will be done by contacting the Randomization Monitor or logging into the web-based randomization system. The unblinded Randomization Monitor will also oversee drug encapsulation and labeling of drug bottles. Replacement doses for subjects who replace dropouts that retain the same ratio of condition assignment will also be created. The Randomization Monitor will provide the investigators with sealed envelopes that will permit emergency unblinding for an individual subject if required. In all other cases, the blind will be maintained up through the primary endpoint assessment. The participant, independent rater and both investigators conducting psychotherapy will be blind to condition assignment, until that point. Participants who drop out of the study or are withdrawn by the Clinical Investigator prior to the primary endpoint will be replaced until blinded data has been collected from 24 participants. Subjects who withdraw during Stage 2 or during the long-term follow-up portion of the study will not be replaced.

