### 12.0 Data Analysis

The Sponsor will judge the clinical and statistical significance of the study and estimate effect size and statistical power based on a comparison of observer-blind data collected at baseline and the primary endpoint using the primary outcome measure, which is the CAPS.

The sample selection is expected to produce acceptably homogeneous groups due to their diagnosis of with PTSD with CAPS scores of at least 50 who have not responded to treatment. There is no expectation that conditions will differ significantly in composition by gender, race or ethnicity, duration of PTSD diagnosis or presence versus absence of other permitted psychiatric disorders, as depression.

The sponsor will examine individual CAPS, BDI-II, PTGI, PSQI, DES-II and GAF scores at baseline and the primary endpoint, in low dose, medium dose and full dose conditions. Descriptive statistics will be calculated for all measurements overall and by condition. Distributional characteristics will be examined for outliers and extreme values and, if either is evident. If outliers are found in primary or secondary outcome measures, the sponsor will perform analyses with and without the outlying data. Effect sizes for all outcome measures for primary endpoint, Stage 1, secondary endpoint, end of Stage 2, and 12-month follow-up will be estimated using Cohen's techniques.

All analyses of data from the primary endpoint will contain blinded data. Analysis of variance will be used to compare Global CAPS scores by dose condition at the primary endpoint.

Analysis of variance, or nonparametric analysis if assumptions are not met, will be used to compare the dose conditions for change in BDI-II, PTGI, PSQI, GAF, DES-II and NEO PI scores separately. If scores cannot be examined sufficiently in this model, then analyses will compare available data through the use of difference scores.

The sponsor will examine open-label data collected two months after the third Stage 1 experimental session. The sponsor will perform a within-subject analysis of full dose participants.

Subjects who discontinue treatment prior to the primary endpoint will be asked to complete an outcome assessment prior to continuing to the long-term follow-up. The data from these subjects will be tested for equivalence to data from subjects completing the study per protocol. If found to be equivalent, data from these subjects will be presented as

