an exploratory intent to treat analysis to examine results without bias towards subjects more likely to complete the study per protocol.

Descriptive statistics will be computed for vital signs and subjective distress during each experimental or open-label session. The sponsor will informally or formally compare peak blood pressure, heart rate and body temperature for participants after sessions after low, medium or full dose MDMA. Frequency tables will be produced on prevalence of spontaneously reported reactions and AEs.

The sponsor will collect Changes in Tinnitus and/or Pain visual analog scale scores from any subject reporting tinnitus or chronic pain during each point of administration, including baseline, experimental and integrative sessions, the primary endpoint, and two-month follow-up. The sponsor will plot and examine all Changes in Tinnitus and/or Pain visual analog scale scores across all three groups and within the dose groups for trends. Formal analysis of Changes in Tinnitus and/or Pain visual analog scale scores will only occur if three or more subjects complete Changes in Tinnitus and/or Pain visual analog scale at baseline and primary endpoint. Likewise, formal between-groups analyses will not be performed if all primary endpoint scores are from subjects assigned to the same condition. The sponsor will perform an independent t-test on the difference between baseline and primary endpoint Changes in Tinnitus and/or Pain visual analog scale scores in the full dose and comparator dose conditions, with p. set at 0.05. If the only scores available are for subjects in a single condition, then a paired t-test will be performed comparing baseline and primary endpoint Changes in Tinnitus and/or Pain visual analog scale scores, with p. set at 0.05.

Descriptive statistics will be computed for SOCQ scores completed after each MDMA-assisted psychotherapy session, and SOCQ scores will be compared across each of the three MDMA dose conditions and after full dose given during Stage 2. The data will be explored for effects of condition on responses to the SOCQ.

Descriptive statistics will be calculated for subject's perceptions of experimental sessions. Mean, standard deviation and range of individual responses will be examined. Perceptions of experimental sessions will be examined during Stage 1 and Stage 2, before and after participant have undergone a third experimental session and will be compared within subjects.

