## **5.0 Randomization and Blinding**

This is a randomized, triple-blind, dose response study with an open-label cross-over segment. For Stage 1, a randomization list will be prepared at the beginning of the study. If needed, subsequent randomization lists will be created to replace subjects who withdraw from the study to ensure that replacement subjects are not added to the end of the initial list. Each subject will be assigned to one of the three dose conditions; 30 mg (low dose), 75 mg (medium dose) or 125 mg (full dose). Twelve evaluable subjects will be assigned to the full dose condition, six evaluable subjects to the 75 mg condition and six evaluable subjects to the 30 mg low dose condition. The study will employ a blinded randomization procedure that will maintain the 2:1:1 ratio while maintaining the blind and ensuring that each subsequent condition assignment is not predicated on the previous assignment.

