## 8.2 Handling of Dropouts, Missing Data

Early termination visit data for ITT and Safety variables will be analyzed at the closest scheduled visit. If the closest visit has valid data, the early termination data will be assigned to the next available visit. If a subject discontinues and does not participate in an early termination visit, data from the last available visit will be used to replace the missing early termination visit data.

Subjects who discontinue treatment prior to completing the second experimental session prior to the primary endpoint will be replaced. These subjects will be asked to complete an outcome assessment prior to continuing to the long-term follow-up. These subjects will be included in the ITT population.

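### Protocol 12.0 shows the exploratory intent-to-treat analysis only if early dropouts pass an undefined equivalence test, while the SAP includes them without condition and names no population for the primary CAPS ANOVA

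*Protocol*

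**What the plan says.** Protocol 12.0 asks subjects who discontinue before the primary endpoint for an outcome assessment. The rule for using it is: "The data from these subjects will be tested for equivalence to data from subjects completing the study per protocol". Only a finding of equivalence leads to the next step, whose status and purpose the protocol describes in these words: "an exploratory intent to treat analysis to examine results without bias towards subjects more likely to complete the study per protocol". The section does not say what happens if equivalence is not found.

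Protocol 5.2 replaces subjects lost before the primary endpoint; they "will be replaced until blinded data has been collected from 24 participants". SAP 5.0 sets the allocation in evaluable subjects: "Twelve evaluable subjects will be assigned to the full dose condition, six evaluable subjects to the 75 mg condition", with six more at 30 mg.

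The SAP contains no equivalence test. Section 8.1 defines ITT as everyone randomized. Section 8.2 says of subjects who stop early and are replaced: "These subjects will be included in the ITT population". Section 8.3 says ITT analyses use all enrolled subjects with whatever data they have. Section 8.9.1 specifies an ANOVA on CAPS-4 change at alpha 0.05 but does not say whether it is run in ITT or per protocol. ITT is expressly assigned only to the disposition and dosing summary (8.6) and to demographics and baseline (8.7).

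**The concern.** The stated purpose of the ITT analysis is to show whether the result is tilted towards subjects who complete. Such an analysis is informative when dropouts differ from completers, yet the protocol's rule presents it only when they are judged not to differ. Whether the check is reported therefore depends on the outcomes it is meant to examine.

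The rule also cannot be carried out as written. Neither document states an equivalence margin, and SAP 8.0 describes only tests of difference at p ≤ 0.05. No dose stratum is named, so dropouts concentrated in one dose group could be compared with a 12:6:6 mix of completers and pass or fail because of dose.

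The trial's product is a set of effect sizes for planning later studies (Protocol 12.1, SAP 6.0). If the ITT result is not shown, any completer bias in those estimates goes forward unexamined.

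**Working it through.** The documents give no margin, dropout rate, CAPS SD or power figure, so there is no stated figure to reproduce. The only arithmetic in the plan, 12 + 6 + 6 = 24 at 2:1:1, is consistent.

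**Inputs.** Completers: 24 (Protocol 5.2). Two-sided level: 0.05 (SAP 8.0). Assumed: k = 2, 3, 4 or 6 dropouts; margins of 0.5 and 1 SD; all differences in SD units (SD = 1).

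**Standard error of the dropout-minus-completer difference.** SE = √(1/k + 1/24), with k + 22 degrees of freedom. For k = 2, 3, 4, 6 this gives 0.736, 0.612, 0.540, 0.456.

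**Reading (a): equivalent means a non-significant t-test.** The pass probability is the noncentral-t probability that |t| stays below its critical value, with noncentrality D/SE. Example: k = 3, D = 1 gives 1/0.612 = 1.63 against a critical value of 2.06 on 25 df; pass probability 0.65.

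| Dropouts | True deficit 0.5 SD | 1 SD | 1.5 SD |
|---|---|---|---|
| 2 | 90% | 74% | 50% |
| 3 | 88% | 65% | 35% |
| 4 | 86% | 57% | 24% |
| 6 | 82% | 44% | 11% |

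**Reading (b): two one-sided tests at 0.05 (TOST), no true difference.** To pass, |observed difference| + t₀.₉₅ × s × SE must be below the margin, where s is the pooled SD estimate. With s = 1 the second term alone is 1.711 × 0.736 = 1.26 for 2 dropouts, 1.708 × 0.612 = 1.05 for 3, 1.706 × 0.540 = 0.92 for 4 and 1.701 × 0.456 = 0.78 for 6. A 0.5-SD margin is therefore out of reach. Simulated pass rates (200,000 draws per cell) are:

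| Dropouts | Margin 0.5 SD | Margin 1 SD |
|---|---|---|
| 2 | 0% | 1% |
| 3 | 0% | 5% |
| 4 | 0% | 15% |
| 6 | 0% | 38% |

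With 24 completers, about 80% power would need about 14 dropouts at a 1-SD margin and about 42 at 0.75 SD; no number suffices at 0.5 SD.

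**Direction of selection under reading (a).** With 3 dropouts truly 1.5 SD worse and no dose effect, the mean observed deficit is about 1.8 SD where ITT is withheld and 0.9 SD where it is shown. In a second simulation, 2 to 4 full-dose dropouts are 1 SD worse than full-dose completers and full beats low by 1 SD. Adding the dropouts moves the full-versus-low effect by −0.13 to −0.21 SD when ITT is shown and by −0.31 to −0.43 SD when it is withheld. The gate passes 85% to 90% of the time in that setting.

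**How often ITT is withheld depends on the dose effect.** For 3 full-dose dropouts 1.5 SD below full-dose completers, reading (a), medium dose midway between the other two:

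| Full minus low | ITT withheld |
|---|---|
| 0 | about 66% (noncentral t: 1 − 0.347 = 65%) |
| 0.5 SD | about 53% |
| 1 SD | about 36% |
| 1.5 SD | about 21% |

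The simulated figures are good to about one percentage point. A dose effect brings full-dose dropouts closer to the pooled completer mean, so they pass more easily.

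**Size of the bias at stake in that case.** Adding 3 such dropouts to 12 completers lowers the full-dose mean by 3/15 × 1.5 = 0.3 SD on average, so the completer mean overstates benefit by about 0.3 SD.

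**The case against.** The best defence is that the SAP already removes the gate. Its ITT definition is unconditional, early dropouts are expressly included, and Protocol 15.0 requires an analysis plan agreed with the sponsor statistician. On that view this is a leftover protocol sentence about an analysis labelled exploratory, in a pilot that SAP 6.0 presents as not powered for its effect. Much of this stands, and it limits the severity. It does not close the point: the SAP says who belongs to ITT but not that CAPS will be reported in ITT, so Protocol 12.0 remains the only text saying when an ITT efficacy result is presented, and that text is conditional.

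A reader might infer that the check appears exactly when it cannot matter and is withheld exactly when it does. That is too absolute. On reading (a), a 1-SD deficit with 3 dropouts passes 65% of the time, so ITT is usually shown despite a real difference. On reading (b), ITT is almost never shown even when dropouts match completers, which is near-blanket omission more than suppression of unfavourable results.

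A reader might also infer that the primary analysis is restricted to completers. The documents do not establish this. Replacement secures 24 evaluable subjects; it does not by itself make the ANOVA per-protocol, and SAP 8.9.1 is silent.

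**Conclusion.** The point holds as a defective rule in Protocol 12.0 and an unresolved conflict with SAP 8.1 to 8.3, compounded by the missing population in SAP 8.9.1. That the gate is conditional, has no margin and works against its own purpose follows from the text and needs no assumption about numbers.

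The sizes do rest on assumptions. A small number of dropouts is plausible for 24 subjects with replacement, but it is not in the documents; nor are the margins, deficits and dose effects. No single withholding rate should be quoted: in the one scenario worked through it runs from about 66% with no dose effect to about 21% if full beats low by 1.5 SD. Nor do the documents show that a result will in fact be withheld; they leave it open. This should be corrected, but the analysis concerned is exploratory and the SAP is already most of the way there.

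**What to change.** 1. In Protocol 12.0, delete the equivalence test and the condition attached to it. Replace them with a statement such as: the CAPS comparison will always be reported in the ITT population of SAP 8.1 (all randomized subjects, by assigned dose, missing data handled as in SAP 8.2) alongside the per-protocol result, and the scores of discontinued subjects will be listed individually.
2. In SAP 8.9.1, name the population for the primary ANOVA and state that the other population is also reported.

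The replacement should not be limited to subjects who have an outcome assessment. SAP 8.1 includes everyone randomized, and SAP 8.2 uses the last available visit when there is no early termination visit. In the Stage 1 schedule CAPS is planned only at screening before the primary endpoint, so for such a subject that value will ordinarily be the baseline. The individual listing lets a reader see where this happened.

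The cost is a few sentences and one more table, with no new data collection, since Protocol 12.0 and 6.3 already seek assessments from discontinued subjects. The reported effect may be slightly less favourable.

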### 12.1 Statistical power

The literature does not provide an estimate of the effect size for change in CAPS after sessions using an low dose or medium -dose MDMA. The proposed study will provide these important estimates. With the current amendment, the sponsor is increasing the group size in each condition, and all subjects will complete the primary endpoint. This may increase statistical power in this study, and will provide important estimates of effect size that can be used to develop a dose response model.

#### 13.0 Informed Consent

The investigator is responsible for obtaining informed consent in adherence to GCP and according to applicable regulations prior to entering the subject into the trial. Information about the study must be given in an understandable form. Written information about the trial will also be provided. In addition to the explanation of evaluation, preparatory, MDMA and integrative psychotherapy sessions, the information should include that access to original medical records and processing of coded personal information must be authorized. The informed consent discussion must be conducted by a person who is qualified according to applicable local regulations. The subject should have the opportunity to inquire about details of the MDMA session and to consider participation.

The informed consent form (ICF) must be signed and dated by the subject and must be countersigned by the investigator. The investigator will provide a copy of the signed ICF to the subject, and will maintain the original in the investigator's study file.

The written ICF and any other written information to be provided to subjects should be revised whenever important new information becomes available that may be relevant to the subject's consent. Any revised written ICF, and written information should receive approval from an IRB before use.

Written consent to take part in the study session includes giving the investigators permission to view the participant's recent medical records to assess protocol eligibility, if needed. Information necessary for protocol participation includes past medical history, psychiatric interview, physical examination, and clinical laboratory tests.

The subject should be informed in a timely manner if new information becomes available that may affect the decision to take part in the MDMA session. The communication of this information should be documented.

Participants can withdraw consent for participation in the protocol at any time without prejudice. If a subject withdraws consent but does not revoke the Health Insurance Portability and Accountability Act (HIPAA) authorization, MAPS will have full access to the subject's medical records, including termination visit information. If a participant revokes only the HIPAA authorization, MAPS will have full access to all of the participant's medical records prior to the date and time of revocation.

### 13.1 Confidentiality

Every effort will be made to strictly safeguard the confidentiality of participants in their role as research participants. Removing identifying information from data and restricting access to researchers directly involved in assessing the participants should prevent the dissemination of confidential data, with or without identifying information. Despite this, privacy cannot be guaranteed. Except for the screening log, the informed consent and a subject contact information sheet that will be stored separately from other documents, all data will be identified only by the participant's initials on the source document and fourdigit subject number. If past medical records are needed, participants will sign forms for the release of information upon consent to permit screening for protocol enrollment. Copies of audio and video recordings intended for sharing with participants will only be marked with the participant's subject number. Any materials mailed to participants will be sent along with stamped return envelopes using the office address of the Clinical Investigator both as main and return address. All assessment records will be kept in a locked file drawer or cabinet in a locked office, and access to measures will be limited to regulatory agencies, researchers, and individuals analyzing data. Researchers, other than the investigators directly involved in the protocol, with access to data will not be provided with any information that would identify participants by name or by other means, such as social security number.

All psychotherapy sessions may be recorded to video and audio. These recordings will be used for manual development and potentially for training therapists to perform MDMA-assisted psychotherapy. They are intended to record the events occurring during therapy, and will not serve as outcome measures. CAPS assessments may also be recorded to video to establish inter-rater reliability. Full names and addresses will not appear in these recordings.

Any use of recordings for purposes other than research or training (e.g. a documentary film) may occur only with separate written informed consent of the participant obtained after study participation is complete.

Maintaining data in a secure environment will prevent the accidental or deliberate examination or removal of data by unauthorized persons. While it is possible that individuals may be identified on audiotape or video recording through means other than their names, restricting access to audio recordings or video recordings to researchers or trainees greatly reduces the risk of a breach of confidentiality.

### 13.2 Costs to Participants

There will be no costs to the study participants for any study-related procedures. The sponsor will cover all costs of study participation, including any assessments or tests performed solely for the purpose of establishing eligibility for participation. Charges for treatment of the participant's condition that are unrelated to the research study or any of its procedures will continue to be billed to the health insurance provider of the participant or to the participant him or herself. It is anticipated that there will not be any charges for treatment that is unrelated to the study except in the case of participants who previously received therapy from the Clinical Investigator and who will continue to receive ongoing treatment that is not related to participating in the study.

